For these reasons, we seek to develop and test a social media based intervention for cannabis use among EAs, delivered by health coaches who will be similar age or slightly

Full Study Title: Harnessing social media to reduce cannabis use among adolescents and emerging adults in an urban emergency department

older peers (i.e. clinical practicum students, bachelor's level psychology students, master's level public health and social work students). The guiding framework for this intervention can be found in Figure 1.

Objective

The specific aims of this clinical trial is to:

Conduct a randomized clinical trial of the SnapCoach intervention, where we will examine feasibility and acceptability of the SnapCoach Intervention as our primary outcome measures. As exploratory, other outcomes we will examine the preliminary efficacy of SnapCoach (vs. usual care control with attention-placebo; N=approximately 50 per group) on cannabis use (quantity, frequency) and consequences.

We will conduct a randomized clinical trial (RCT), to examine the feasibility, acceptability, and initial efficacy of the SnapCoach intervention. Our goal is to recruit N = 100 participants (as our target N) meeting eligibility criteria, who will complete baseline measures, and be randomized to receive the SnapCoach intervention or a control condition. They will participate in the 4-week intervention/control condition, with a post-test administered at 1-month post-baseline (i.e., end of 4-week intervention period) and a follow-up assessment of outcomes at 3-months post-baseline.

Primary outcomes are feasibility and acceptability of the Snapcoach intervention. Other exploratory outcomes include measures of cannabis quantity and frequency and consequences measured at the 3-month follow-up, examining the effect of the intervention on other substance use (alcohol, other drugs), analyses of moderators and mediators (e.g., sex, cannabis use motives), identification of the most engaging intervention content, dose-response analyses, and measurement of intervention delivery costs.

Aim 2 Methods:

Enrollment

Target enrollment is 100 emerging adults (approximately 50% males and 50% females) between the ages of 18-25, in a 2-arm pilot RCT of SnapCoach compared to an enhanced usual care (EUC) with attention placebo for EAs with weekly cannabis use.

Recruitment Procedures

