remotely, they will not complete the UDS during the baseline procedures. For these remote participants, and when an in-person participant does not complete the UDS during baseline procedures for any other reason, those participants will still be compensated a total of \$40. Our consents do not reflect that a participant will still receive \$40 if they do not complete the UDS because doing so could adversely affect UDS completion rates among participants who would otherwise be willing to complete the test. Participants will also complete their assigned condition (i.e., *SnapCoach* initial session or EUC: review of health and community resources, with the same information contained in a paper brochure or electronic format depending on type or recruitment). Enrolled participants may also receive small items such as candy, water bottles, notebooks, etc., or small tchotchkies with project logo and phone number (e.g., lanyard or pen) during the study. These tokens are not used as a contingency of study participation.

For those assigned to the intervention condition, the *SnapCoach* initial session is an intervention delivered in the ED and/or remotely (e.g., facetime, bluejeans, vidyo, or Skype for Business) by research health coaches using a computer. The health coaches will use a computerized guide and Motivational Interviewing (MI) to engage EAs and understand their cannabis use. Sessions will be followed by reviewing a health and community resources that the participants keep (provided electronically or on paper, dependent on type of recruitment). This session will take about 30-45 minutes and will be audio-recorded.

Participants will receive pre-selected snaps, up to 3 per day, from health coaches over 4 weeks. The final Snapchat content was created based on focus testing participant ratings and feedback and/or engagement data, and uses the Why/How model of MI. Messages address 1) Why (evoking reasons for change), and/or 2) How (Tools for change). We also send encouraging greetings/affirmations to enhance engagement.

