in overestimation of the treatment effect when there are multiple follow-up points. It has been shown that baseline adjustment at only the first follow-up (1M in this case) corrects this overestimation while also guarding against regression to the mean, which will be our approach. Within this framework, we will conduct exploratory sub-analyses of whether the intervention effect is accumulating or weakening over time, by including time-by-group interactions. If the need is ascertained, we will control for confounders through their inclusion in the model as covariates. Our initial specification will be a linear mixed effects model (with Gaussian error distribution) with only a random intercept to capture within-individual dependence, but this choice will be scrutinized by examining model diagnostics and evaluating the veracity of modeling assumptions. As the need is ascertained, we will examine other distributional choices (e.g., Poisson, Negative Binomial) and more complex random effects structures (e.g., autoregressive).

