Aim 2: The sample size is $N = 100$ (approximately 50 per group). For our primary analytic goal – examining feasibility and acceptability this is acceptable. With regard to other exploratory analyses estimating treatment effects – we are comparing two groups of size $n = 50$. Assuming no substantial covariate adjustment is needed, testing the significance of the treatment effect at a single time point will be equivalent to the comparison of two means, for which we use Cohen's D (0.2: small, 0.5: medium, 0.8: large) as an effect size. Under the expected sample size, we will have sufficient power ($>80\%$) to detect effects on both our cannabis and other substance use outcomes if $d > 0.56$, a medium effect size. Although the required effect size is non-negligible, the proposed pilot will provide the critical data necessary to inform the power analyses for a subsequent efficacy trial. While effect sizes from pilot studies

Full Study Title: Harnessing social media to reduce cannabis use among adolescents and emerging adults in an urban emergency department

can have large standard errors and be unstable,²⁰² we can use these pilot data to estimate point estimates and confidence intervals for our treatment effect sizes using the R package MBESS²⁰³.

Data Confidentiality Plans

Our study team will take the following steps to minimize potential confidentiality breaches. As done in prior research and deemed HIPAA compliant by the IRBs at University of Michigan (UM) and HMC by use of a waiver of HIPAA authorization, minimal clinical data will be collected on ED patients who refuse to participate in the screening survey, and on ED patients who the research assistants fail to approach or contact (for remote recruitment). ED-based intervention, TLFB assessment sessions and any phone interviews (e.g., in the event a person cannot attend a follow-up in person, or during remote recruitment, we can administer the TLFB by phone) will be audio-recorded and will be destroyed after the conclusion of the study.

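### The first-choice t-test, the initial mixed model and the power figure assume no coach effect, although only the SnapCoach arm receives a coach-delivered motivational interviewing session

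*Combined protocol and SAP*

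**What the plan says.** The background section describes the coaches as peers of similar or slightly older age with mixed training, among them "clinical practicum students, bachelor's level psychology students" and master's-level students. Under Study Procedures, the SnapCoach initial session lasts 30-45 minutes, uses motivational interviewing and is "delivered in the ED and/or remotely (e.g., facetime, bluejeans, vidyo, or Skype for Business) by research health coaches using a computer". The control arm reviews a resource brochure and has no such session. Both arms add the coaches on Snapchat for four weeks. Controls receive messages without intervention content, and coaches reply to SnapCoach participants during shifts.

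Under Data Management and Analysis, the first-choice test of the exploratory outcomes is a two-sample t-test on the change from baseline to 3 months. The mixed model begins "with only a random intercept to capture within-individual dependence". That choice is to be checked against diagnostics, and more elaborate random effects may follow. The one example given is autoregressive, a within-person structure.

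Under Power calculation and sample size, "testing the significance of the treatment effect at a single time point will be equivalent to the comparison of two means". There, "we are comparing two groups of size $n = 50" per arm, and power above 80% is claimed for "outcomes if $d > 0.56$, a medium effect size".

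The documents do not give the number of coaches, how they are assigned, a coach ICC or a design effect. They do not say that the coach who delivers each initial session will be recorded; the coach log under Study Procedures is described for Snapchat messages.

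**The concern.** Participants whose initial session is given by the same coach may resemble one another in outcome, because coaches can differ in skill and style. The design is then partially nested: SnapCoach participants are grouped by session coach and controls are not. A t-test or a participant-intercept model leaves the between-coach variance out of the standard error of the arm difference. Confidence intervals are then too narrow and type I error exceeds its nominal level.

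Efficacy is exploratory here, so no confirmatory claim is at risk. What is at stake is the next trial. The power section says that effect-size estimates and their confidence intervals from this pilot will feed the power analysis of a later efficacy trial. Intervals that omit coach variation would make those estimates look more certain than they are. The t-test has no place for a coach term, and if the session coach is not recorded the question may not be answerable afterwards, since the recordings are to be destroyed when the study ends.

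**Working it through.** **Inputs from the documents:** 50 per arm; d = 0.56 in SD units; power above 80%.

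**Assumptions, because the documents are silent:** two-sided alpha of 0.05 (this reproduces the stated figure; one-sided 0.05 would give 87.6%); no dropout, as in the plan's own figure; 3 to 10 coaches with equal caseloads, and 5 coaches with 10 sessions each as the worked case; coach ICC 0.01 to 0.10; each SnapCoach participant has one session coach; no coach clustering in controls.

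**Step 1: the plan's figure.** The SE of the difference is sqrt(2/50) = 0.200. Power = Φ(0.56/0.200 − 1.96) = Φ(0.84) = 79.96%. With a t distribution on 98 df it is 79.2%. The detectable d at 80% power is 0.560 (normal) or 0.566 (t). The stated figure reproduces, with participants taken as independent.

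**Step 2: partial nesting.** With k coaches:

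- SnapCoach design effect: DE = 1 + (50/k − 1) × ICC; control: 1
- Variance inflation of the difference: V = (DE + 1)/2
- True SE relative to reported SE: sqrt(V)
- Type I error of the unadjusted test: 2 × [1 − Φ(1.96/sqrt(V))]
- Power of a correctly calibrated test: Φ(0.56/(0.200 × sqrt(V)) − 1.96)

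For k = 5 and ICC 0.05: DE = 1 + 9 × 0.05 = 1.45; V = 1.225; sqrt(V) = 1.107; type I error 7.7%; power = Φ(2.53 − 1.96) = 71.6%.

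| Coaches | ICC | DE | True SE ÷ reported SE | Type I error | Power at d = 0.56 |
|---|---|---|---|---|---|
| 8 | 0.01 | 1.05 | 1.013 | 5.3% | 78.9% |
| 5 | 0.02 | 1.18 | 1.044 | 6.0% | 76.5% |
| 5 | 0.05 | 1.45 | 1.107 | 7.7% | 71.6% |
| 5 | 0.10 | 1.90 | 1.204 | 10.4% | 64.3% |

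The SE ratios mean that the true SE is 4%, 11% and 20% larger than reported in the three 5-coach rows. Put the other way, the reported SE is 4%, 10% and 17% too small.

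**Step 3: simulation.** With 20,000 replicates of the unadjusted t-test and 5 coaches, type I error was 6.1%, 7.5% and 10.5% at ICC 0.02, 0.05 and 0.10, in line with the formula.

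**Step 4: small number of coaches.** With Satterthwaite degrees of freedom and 5 coaches, power at d = 0.56 is 69.8%, 63.5% and 54.7% at the same ICCs, so the normal-approximation losses are the milder version. Even at ICC 0 the coach-level degrees of freedom bring power to 74.4%. Over 3 to 10 coaches and ICC 0.01 to 0.10, normal-approximation power runs from 79.2% down to 55.4%.

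**The case against.** There are five fair objections.

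- **The model is not closed.** A reader might infer from the quoted words that the plan permits only within-person dependence. It does not say that. The words describe a starting specification, to be checked and extended if needed. A coach effect is unplanned, not excluded. This stands, although the examples of dependence are all within-person and the t-test comes first.
- **Controls also have coaches.** A reader might infer that coach contact is confined to SnapCoach. Under Study Procedures, controls add the coaches and receive messages from them, and shift work means that one participant may deal with several. This stands: it may dilute clustering in the messaging phase, and a coach effect common to both arms would partly cancel. The nesting argument applies mainly to the initial session. Even there, one coach per participant is a fair reading but is not written.
- **Correlation is not shown.** The documents give no ICC, and a computer-based guide, snaps chosen in advance, coach training and supervision may all limit coach variation. This stands; the size of the effect is conditional on assumptions.
- **The primary outcomes are descriptive.** A reader might infer that the precision of session acceptability is overstated. No interval, test or threshold is planned for it, so there is no stated precision to correct. The point applies only if an interval is reported.
- **The ICC will be poorly estimated.** With 5 coaches and 10 sessions each, an estimated ICC of 0.05 has an F-based 95% interval of about −0.05 to 0.54; with 8 coaches, about −0.09 to 0.43. This stands and must be said in the report. It does not remove the case for recording the coach and showing how far the treatment-effect interval moves.

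**Conclusion.** The concern holds in a limited form. The first-choice test, the initial mixed model and the power figure all assume zero coach variance, while one arm alone receives a coach-delivered session. Under the assumed 5 coaches, the true SE of the arm difference would be 4% to 20% larger than reported for ICC 0.02 to 0.10, with type I error of 6.0% to 10.4% and power of 76% to 64% at d = 0.56. With 8 coaches and ICC 0.01 there is almost nothing to correct.

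These figures assume that nesting by session coach carries through to the 3-month outcomes, which shared messaging may weaken. A reader might conclude that the power claim is miscalculated. It is not: it reproduces, and what is missing is the condition it rests on. Because efficacy is exploratory and the primary outcomes are descriptive, this is an inexpensive improvement to the plan and not a flaw in its main conclusion.

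**What to change.** 1. Record the ID of the coach who delivers each initial session, and state how many coaches there are and how they are assigned.
2. Prespecify a sensitivity analysis of the exploratory treatment effects with a random effect for the initial-session coach in the SnapCoach arm only, controls as singletons, and small-sample degrees of freedom.
3. Report the coach ICC with its interval, and say that it is very imprecise with few coaches.
4. Add to the power sentence that it assumes no coach clustering.
5. If an interval is reported for session acceptability, allow for coach clustering in it.

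The cost is one data field, one extra model and a few words. The downside is wider treatment-effect intervals, partly from the small coach-level degrees of freedom even if the ICC is zero, and an ICC too imprecise to be used alone in planning. Sample size and trial conduct do not change.

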There will be two follow-up assessments, at 1-month and 3-months post-baseline assessment. After the 4 weeks of interacting with health coaches on Snapchat, participants will be completing a 20-minute online, video, phone or in-person (depending on participant preference) 1-month follow-up assessment (\$25), and an in-person, online, video or phone (depending on participant preference) 3-month follow-up assessment which includes a web-based survey, the RA-administered TLFB, and a UDS (if in-person) to encourage accuracy of substance use reporting. Participants will receive \$40 for the 3-month assessment. When a participant is recruited remotely, they will not complete the UDS for the 3-month assessment. For these remote participants, and when an in-person participant does not complete the UDS at the 3-month assessment for any other reason, those participants will still be compensated a total of \$40. Follow-up assessment reminders will be sent in a variety of ways which may include via e-mail, private Snapchat messaging, SMS text message, mail and/or phone call and other social media, based on contact information participants provide at the enrollment assessment. Three-month follow-up assessments completed in-person may be done at the HMC, or other community locations for participant convenience. During the RA-administered TLFB, the participants will view pictures and response cards either on paper (when in person) or given the option to view them electronically when completed over the phone (sent to the participant via preferred method, e.g., email, text, or in a shared online document, etc.). The RA-administered TLFB and intervention sessions will be audio-recorded. Whenever possible, follow-up staff completing assessments will be blinded to condition assignment.

Measures

We will use reliable, valid measures from prior work with EAs, reflecting our conceptual model: demographics; SM involvement; cannabis use, motives, and consequences; and protective strategies, etc. (Table 1). Some measures (e.g., intervention ratings) were created for use in this study.

Full Study Title: Harnessing social media to reduce cannabis use among adolescents and emerging adults in an urban emergency department

Table 1. Measures.
 
(S=Screening, B=Baseline, I=Immediate Post-test, 1M=1-month follow-up, 3M=3-month follow-up)
	

Individual Level and Descriptive Characteristics
	

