Demographics: Age, Sex, Race, Ethnicity (adapted from national surveys, e.g., the Youth Risk Behavior Survey ³⁹)	S
Demographics: Gender identity, Sexual Orientation, School Status, Employment, Living Situation, Children, Marital Status, Pregnancy (adapted from national surveys, e.g., the Youth Risk Behavior Survey ³⁹)	B,3M
Demographic: Parents and Personal Income ^{86,87}	B
Service Utilization: ER and Urgent Care ^{86,87}	B,3M
1-minute delay discounting task ⁸⁴	S,1M,3M
Snapchat involvement (modified) ^{22,40,41,42}	S
Comprehensive Marijuana Motives (modified) ⁴³	B,3M
Perceived risk of cannabis (modified for different cannabis modalities) ⁴⁴	S,1M,3M
Importance, Self-Efficacy, Intention Rulers ^{45,46}	B,I,1M,3M
Cannabis acquisition, strain, and medical marijuana ^{47,48,49,50,51,74}	
Cannabis acquisition	B,1M,3M
Preferred Marijuana Strain	B
Medical Marijuana	S,3M
NIDA modified ASSIST ^{65,66,85}	S,3M
Alcohol use frequency (AUDIT-C) ⁷³	S,3M
Tobacco and Nicotine use (modified) ⁶⁵	S,1M,3M
Mental health: Patient Health Questionnaire-2; Generalized Anxiety Disorder-2 ^{52,53,54,55,56,57,58,59,60,61}	B,1M,3M
Protective Behavioral Strategies for Marijuana (modified) ⁷⁷	B,3M
Gun Carriage ^{75,76}	B
Hope ⁷⁸	B,1M,3M

Peer/Social Influences
	
Cannabis online norms and exposure ^{64,41}	B,1M,3M

Exploratory Outcomes
	

Full Study Title: Harnessing social media to reduce cannabis use among adolescents and emerging adults in an urban emergency department

Cannabis use method, frequency and quantity ⁷⁴ (modified) Smoke, Vape, and Dab (frequency, quantity) Drink and all methods combined (frequency, quantity) Number of days all methods combined Number of days vaped	S,3M B,3M B,1M,3M 1M
Cannabis and Other Drug Use Frequency, Alcohol Quantity/Frequency(TLFB) ^{67,68,69,70}	B,3M
Brief Marijuana Adolescent Consequences Questionnaire (modified) ⁷¹	B,3M
Impaired driving (modified) ⁷²	B,3M
Primary Outcomes: Feasibility/Acceptability of Intervention	
Brief Intervention acceptability ratings (created for this study)	I
Snapchat acceptability ratings (created for this study)	1M
Brief intervention feasibility (e.g., % of participants completing brief intervention)	I
Snapchat health coaching feasibility (e.g., % of participants who complete process of adding health coach on Snapchat, % of participants who reply to at least 1 Snapchat message)	I,1M

Data Management and Analysis

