Other analyses. *Moderation:* To assess potential moderators we will include interactions with treatment group in the GLMM models above. Potential effect modifiers will include sex and age. *Mediation:* To test if cannabis motives and other variables (e.g., mental health symptoms) mediate treatment effects, we will use Imai's causal mediation analysis framework, that is robustly implemented in the R package *mediation*. Traditional mediation analysis can be susceptible to bias; one source of this bias is the limitation to the classes of statistical models (e.g. the linear structural model of Baron and Kenny), that can be accommodated in traditional mediation analysis. Under technical assumptions of sequential ignorability, mediation effects are identifiable using Imai's framework when models for the mediator and for the outcome that are non-linear, have discrete (nominal or ordinal) or continuous outcomes, include random effects, or are non-parametric. *Engagement:* Daily content ratings assessed by tallies from Snapchat messages logs (e.g., content, messages sent/received) will be calculated for different content areas (e.g., free time, stress, drug/alcohol-related) and assessed descriptively to see types of content with high response rates. *Cost:* To estimate intervention we will calculate summary statistics for the total intervention-specific costs and mean costs per participant, with confidence intervals. Costs will be reported with/without start-up and development, for example, including costs for recruiting and training coaches as well as their clinical supervision. As with prior work, net costs (savings) will be calculated by subtracting mean costs per participant in the control group from costs per participant for the assigned condition, also calculating the incremental cost effectiveness ratio (difference in mean cost of intervention vs. control divided by difference in mean effectiveness between intervention and control). Change in health benefits will be measured as the difference in cannabis consequences per month for the intervention vs. the control, expressed in dollars per consequence averted. Sensitivity analyses to evaluate alternate assumptions for estimated costs will be conducted. Given likely skewness, we will identify appropriate methods for generating confidence intervals that do not rely on the normal distribution (e.g., non-parametric bootstrapping).

Power calculation and sample size

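### Cannabis motives are read after randomisation only at 3 months, so the exploratory mediation analysis cannot tell motives changing use from use changing reported motives

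*Combined protocol and SAP*

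**What the plan says.** All places are in the combined protocol and SAP.

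- Data Management and Analysis, Other analyses (Mediation): a causal mediation framework is to be used "To test if cannabis motives and other variables (e.g., mental health symptoms) mediate treatment effects". Identification rests on sequential ignorability. No visit is named for any mediator, and the only sensitivity analyses in that paragraph concern costs.
- Table 1, row "Comprehensive Marijuana Motives (modified": coded B,3M.
- Table 1, row "Mental health: Patient Health Questionnaire-2; Generalized Anxiety Disorder-2": coded B,1M,3M.
- Objective: the exploratory outcomes are "cannabis quantity and frequency and consequences measured at the 3-month follow-up". In Table 1 the row "Cannabis and Other Drug Use Frequency, Alcohol Quantity/Frequency(TLFB" and the consequences scale are both B,3M. Days of use by all methods is B,1M,3M, and days vaped is 1M.
- Study Procedures: the baseline survey is completed before randomisation.
- Objective: the 1-month assessment falls at the end of the 4-week intervention. Mediator analyses are listed among the exploratory outcomes.

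**The concern.** A mediator has to be moved by treatment and then move the outcome. Baseline motives precede randomisation and can only be a covariate or a moderator. The 3-month reading is taken at the visit that supplies the outcomes, so a person who has cut down for some other reason may simply report different motives. The data would look the same as if changed motives had reduced use.

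A concurrent association could therefore be reported as a mechanism. The section on power and sample size says the pilot is meant to inform a later efficacy trial, and a mislabelled mechanism could steer that design.

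**Working it through.** **1. The schedule**

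| Measure | Before randomisation | 1M | 3M |
|---|---|---|---|
| Motives | B | no | yes |
| Mental health symptoms | B | yes | yes |
| TLFB frequency; consequences | B | no | yes |
| Days of use, all methods | B | yes | yes |
| Days vaped | none | yes | no |

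Motives readings after randomisation: one. Motives readings after randomisation and before any follow-up outcome visit: none. For the 1-month use-day items, the motives reading comes after the outcome. Mental health symptoms do have a reading that precedes the 3-month outcome.

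**2. The plan's own figure**

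The plan states more than 80% power at d above 0.56 with 50 per group. Two-sided alpha of 0.05 is assumed, since none is given. Then 0.56 × √(50/2) = 2.80, 2.80 − 1.96 = 0.84, and Φ(0.84) = 0.80 (0.79 by the exact t-test). It reproduces, and the present point does not depend on it.

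**3. Spurious share when nothing is mediated (illustration)**

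The documents give none of these inputs. Assumed:
- Use has SD 1, and treatment shifts it by τ = 0.5 at both follow-ups.
- Motives = p × same-visit use + independent noise of variance 1 − p², with p = 0.3 or 0.5.
- Correlation of use between adjacent visits is ρ = 0.5 or 0.7. Correlation from baseline to 3M is κ, with κ = ρ (equal) or κ = ρ² (decaying).
- Models are linear and adjust for baseline motives and baseline use.

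The treatment effect on motives is pτ. Multiplying by the fitted motives slope and dividing by τ gives the share:
- Same visit: p²(1 − κ²) / [p²(1 − κ²) + 1 − p²]
- 1M motives, 3M use: p²ρ(1 − κ) / [p²(1 − ρ²) + 1 − p²]

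| p | ρ | Structure | Same visit | 1M to 3M |
|---|---|---|---|---|
| 0.3 | 0.5 | equal | 0.0675/0.9775 = 6.9% | 0.0225/0.9775 = 2.3% |
| 0.3 | 0.7 | equal | 0.0459/0.9559 = 4.8% | 0.0189/0.9559 = 2.0% |
| 0.3 | 0.5 | decaying | 0.0844/0.9944 = 8.5% | 0.0338/0.9775 = 3.5% |
| 0.3 | 0.7 | decaying | 0.0684/0.9784 = 7.0% | 0.0321/0.9559 = 3.4% |
| 0.5 | 0.5 | equal | 0.1875/0.9375 = 20.0% | 0.0625/0.9375 = 6.7% |
| 0.5 | 0.7 | equal | 0.1275/0.8775 = 14.5% | 0.0525/0.8775 = 6.0% |
| 0.5 | 0.5 | decaying | 0.2344/0.9844 = 23.8% | 0.0938/0.9375 = 10.0% |
| 0.5 | 0.7 | decaying | 0.1900/0.9400 = 20.2% | 0.0893/0.8775 = 10.2% |

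The true share is 0 throughout. A simulation of the same model (50 per arm, 3,000 runs per setting, Monte Carlo 95% interval for the indirect effect) agreed with these shares. The same-visit interval wrongly excluded zero in 6% to 9% of trials at p = 0.3 and 24% to 25% at p = 0.5. For the lagged analysis the figures were 1% to 2% and 6% to 14%.

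**4. Price of the lagged analysis if motives act on use without delay**

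Assume treatment shifts motives by 0.5 SD, motives act on same-visit use with slope p, the total effect is 0.5, and motives correlate 0.5 between adjacent visits. The true share is p, that is 30% or 50%, and the same-visit analysis recovers it. The lagged slope is p × 0.5(1 − κ)/(1 − 0.25):
- Equal correlation (κ = 0.5): the factor is 0.25/0.75 = 1/3, so the lagged share is 10% or 17%.
- Decaying correlation (κ = 0.25): the factor is 0.375/0.75 = 1/2, so the lagged share is 15% or 25%.

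In simulation the lagged interval excluded zero in 13% to 23% of trials at p = 0.3 and 31% to 52% at p = 0.5. The same-visit interval did so in 61% to 77% and 71% to 80%.

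**The case against.** The strongest objection is that the remedy is a trade. If motives act without delay, the same-visit analysis is the unbiased one, and the lagged analysis recovers only a third to a half of the effect with low power. If use drives motives, the lagged analysis is still biased. This stands. It is a reason to report both results with their limits, not to leave the 3-month result labelled as mediation.

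Second, an extra motives questionnaire at 1 month may itself influence behaviour. The Potential Benefits section accepts that assessments can act as a slight intervention. This also stands, though it would apply to both arms.

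Third, the analysis is exploratory and the plan makes identification conditional on assumptions. That limits the consequence. It does not answer the point, because sequential ignorability concerns confounding and takes the order of mediator and outcome as given.

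Fourth, some cannabis items are read at 1 month. True, but no motives reading precedes them after randomisation.

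Stronger readings that the documents do not support:
- A reader might infer that every mediator is affected. Mental health symptoms have a 1-month reading; what is missing there is only the statement of which visit is used.
- A reader might count protective behavioural strategies, also B,3M, as a second affected mediator. The mediation paragraph does not name it.
- A reader might treat unstated recall windows as a defect. The instruments are cited but not supplied, so this is weak evidence.
- A reader might infer that a 1-month reading would establish direction. Step 3 of the working shows that some bias remains.

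**Conclusion.** The concern holds on the schedule: motives are a named mediator, and no motives reading falls between randomisation and any follow-up outcome visit. Confidence is high for that fact only.

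The magnitudes rest wholly on assumed paths and correlations. At a path of 0.3 the false-positive rate is close to nominal, and the problem becomes material toward 0.5, where about one trial in four would show an indirect effect that does not exist. A 1-month reading reduces the spurious share by roughly half to two thirds in these settings and does not remove it.

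It would go too far to say that this threatens the trial's findings. Feasibility and acceptability are the primary outcomes, and neither they, the treatment-effect estimates nor the sample size depend on the mediation analysis. Severity: consider.

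**What to change.** 1. Add the motives scale to the existing 1-month survey.
2. In the mediation paragraph, name the visit that supplies each mediator and each outcome. For mental health symptoms, use the 1-month reading already scheduled.
3. Report the analysis of 1-month mediator and 3-month outcome, adjusted for the baseline (or screening) values of both. Beside it, report the 3-month motives result labelled as a concurrent association.
4. State that the lagged analysis reduces but does not remove bias from reverse causation. State also that it is attenuated and has low power at 50 per arm if motives act without delay, so a null lagged result is not evidence against mediation.
5. If the schedule is closed, omit step 1 and report the motives result only as a concurrent association.

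Cost: steps 2 to 5 are wording and reporting only. Step 1 lengthens a survey planned at 20 minutes by an amount the documents do not allow one to state, and adds some possible assessment reactivity in both arms.
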